6 STUDY DESIGN

6.1 Overview

This feasibility study is a prospective, multi-center, single-arm, open label study designed to assess the safety and feasibility of the use of the Levita

Robotic Platform with the Levita Magnetic Surgical System in laparoscopic procedures.

6.2 Sample Size and Number of Centers

The study will be conducted at up to five (5) clinical sites with a target maximum of 100 subjects in which the Robotic Platform and Levita Magnetic Surgical System is used for laparoscopic procedures.

6.3 Study Duration

Enrollment of subjects in this study is anticipated to take up to 12 months. Clinical follow-up evaluations will be conducted at discharge, and 7 and 30 days following surgery. The total study duration is expected to be approximately 13 months.

7 STUDY PROCEDURES

7.1 Subject Eligibility, Pre-Screening, and Exclusions

All subjects presenting for elective laparoscopic procedures are potential candidates, and will be screened for eligibility. Study clinicians will select subjects based on knowledge/experience. A Screening/Enrollment Log will be provided to the study sites to maintain a cumulative tracking of all screened subjects.

Subjects must meet all study entrance criteria for enrollment in the clinical study. Reasons for screening failure(s) will be documented.

7.1.1 Inclusion Criteria

Subjects must meet ALL of the following inclusion criteria to be eligible for participation in the study:

1. Subject is at least 18 years of age
2. Subject is scheduled to undergo elective laparoscopic procedure
3. Subject signs a written Informed Consent Form (ICF) to participate in the study prior to any study required procedures

7.1.2 Exclusion Criteria

Subjects must be EXCLUDED from participation in this study if ANY of the following exclusion criteria are met:

1. Subjects with pacemakers, defibrillators, or other electromedical implants
2. Subjects with ferromagnetic implants
3. Subjects with significant comorbidities: cardiovascular, neuromuscular, chronic obstructive pulmonary disease, and urological disease (renal failure)

4. Subjects with clinical history of impaired coagulation confirmed by abnormal blood tests
5. Subject has an anatomical abnormality or disease of intended target tissue noted after initiation of index procedure that would prevent device use
6. Subject is pregnant or wishes to become pregnant during the length of study participation
7. Subject is not likely to comply with the follow-up evaluation schedule
8. Subject is participating in a clinical trial of another investigational drug or device

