2 SURGICAL SYSTEM DEVICE DESCRIPTION

The MSS is composed of three components: the Detachable Grasper, the Delivery/Retrieval Shaft (together, the “Magnetic Grasper Device”), and an external Magnetic Controller mounted on a Robotic Platform.

The Detachable Grasper and Delivery/Retrieval Shaft make up the Magnetic Grasper Device (**Figure 1**). Once the Magnetic Grasper Device is inserted through an access port and the Grasper is attached to the desired tissue, the Detachable Grasper can be detached from the Delivery/Retrieval Shaft and controlled externally using the Magnetic Controller. Traction of the tissue is maintained through the magnetic field attraction between the Detachable Grasper and the Magnetic Controller. The Magnetic Grasper Device is operated by hand and is inserted into the abdominal cavity through a ≥ 10 mm laparoscopic trocar port. The Magnetic Grasper Device is single-use, disposable, and provided sterile to the user.

[figure not shown]

Figure 1. Magnetic Grasper Device

The Magnetic Controller mounted on the robotic arm (**Figure 2**) emits a magnetic field that attracts the Detachable Grasper. Once the Detachable Grasper is attached to the desired tissue/organ and detached from the Delivery/Retrieval Shaft, the robot arm brings the Magnetic Controller to the external surface of the abdominal wall so that it can magnetically couple to the internal Detachable Grasper. Under control of the surgeon, the LRP moves the Magnetic Controller along the surface of the abdomen. When the Magnetic Controller moves, the Detachable Grasper follows, thus retracting the internal tissue/organ to a location of the surgeon's choice. The external Magnetic Controller and the LRP is reusable, provided non-sterile to the user, and must be placed in an off-the-shelf sterile bag prior to use.

[figure not shown]

Figure 2. Magnetic Controller

The Levita Robotic Platform (**Figure 3**) includes two robotic arms, control unit(s), and control software. A handheld and/or foot-operated control pad allow for LRP control by the surgeon or surgical assistant. One arm of the LRP attaches the Magnetic Controller using the arm mount of the Magnetic Controller and the second robotic arm attaches a conventional laparoscopic camera.

[figure not shown]

Figure 3. Levita Robotic Platform. One arm is mobilizing the External Magnetic Controller (external magnet) and the second arm is mobilizing a conventional laparoscopic camera.

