5 STUDY ENDPOINTS

The following endpoints will be evaluated in all subjects who undergo laparoscopic procedures using the Robotic Platform and Magnetic Surgical System.

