5.2 Feasibility Outcomes

Ability to utilize the Levita MSS with the LRP as intended in laparoscopic procedures. The following outcomes will be considered in this feasibility study:

1. The LRP is able to engage, move, and decouple with the MSS as intended / controlled by the surgeon
2. The LRP is able to provide adequate endoscopic visualization via a conventional endoscopic system as intended / controlled by the surgeon
3. The procedure is successfully performed with the MSS and LRP.
4. The MSS or the LRP cannot be successfully used and due to a MSS or LRP performance issue the procedure must be converted to an open procedure.

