5.3 Other Assessments

- Operative time
- Time spent in the Post Anesthesia Care Unit (PACU)
- Length of stay (LOS) (time from admittance to post-anesthesia care unit until hospital discharge)
- Conversion rate (conversion to an open procedure due to inadequate MSS performance)
- Number of required surgeons
- Estimated blood loss
- MSS and Robotic Platform malfunctions
- Patient and Surgeon satisfaction with the system

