9.2 Sample Size Justification

This is a single-arm, multi-center, investigational study to understand the safety and feasibility of the use of the LRP with the MSS. A sample size of 100 subjects was planned to allow use of the system in a number surgeons and a number of different types of laparoscopic procedures. It is expected that enrollment of 100 subjects will provide appropriate information regarding the safety and feasibility of the LRP and MSS in laparoscopic procedures.

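### Exclusion 5 can be met only after surgery has started, so anatomy-related non-use can leave the feasibility denominator without being reported beside the results

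*Combined protocol and SAP*

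**What the plan says.** Section 7.1.2 (repeated in the synopsis) lists as exclusion 5: "Subject has an anatomical abnormality or disease of intended target tissue noted after initiation of index procedure that would prevent device use". The lead-in to the list makes any one criterion enough to exclude a subject from participation, with no separate rule for a criterion met on the operating table.

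The endpoint population is set in the opening line of section 5: "The following endpoints will be evaluated in all subjects who undergo laparoscopic procedures using the Robotic Platform and Magnetic Surgical System". Section 6.2 counts subjects in a similar way, as a "target maximum of 100 subjects in which the Robotic Platform and Levita Magnetic Surgical System is used for laparoscopic procedures".

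Among the feasibility outcomes in section 5.2, outcome 3 is a procedure successfully completed with both devices. Outcome 4, the only one worded as a failure, applies when a device "cannot be successfully used and due to a MSS or LRP performance issue the procedure must be converted to an open procedure". The conversion rate in section 5.3 is limited to conversions blamed on poor MSS performance.

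On timing, section 7.1 states: "Subjects must meet all study entrance criteria for enrollment in the clinical study". Section 8.3 likewise places the check against the criteria before study entry. Section 7.6 asks every subject to return at 7 and 30 days.

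Section 9.1 describes the study as not intended to provide statistical data, allows for descriptive tables, and defines no analysis set.

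**The concern.** Whether the devices can be used once the surgeon sees the anatomy is part of what a feasibility study is meant to show. Here a subject can consent, be anaesthetised and have the operation started, and then be excluded because the target tissue does not permit device use. If that subject is then outside the section 5 population, the reported success rate is conditional on the anatomy having proved suitable during surgery. The condition works in the device's favour, since it can remove non-successes but not successes.

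The opening line of section 5 also governs the safety outcomes in section 5.1. Adverse events in such a subject would still be recorded under sections 12.1.1 and 12.2, but it is unclear whether they would enter the safety summary, or whether the subject would be seen at days 7 and 30.

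**Working it through.** **1. Where an exclusion-5 case can go.** Take a consented subject in whom surgery starts and the anatomy then rules out the devices.

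- *Section 5 population:* requires a procedure using both devices. If neither was used, the subject is out. If they were tried and abandoned, the answer depends on what counts as using them, which the plan does not define.
- *Outcome 3:* would show a non-success, but only if the subject is still in the section 5 population.
- *Outcome 4:* needs a device-performance cause and conversion to open surgery. Unsuitable anatomy is not a performance issue, and the operation may be finished laparoscopically by conventional means.
- *Conversion rate, section 5.3:* needs inadequate MSS performance, so it does not apply.
- *Records:* the screening and enrolment log (section 7.1), the intra-operative items on device observations, conversion and additional tools (section 7.4) and the Study Termination form (section 7.8) could each hold the reason. The plan names none of them for this case and does not ask for a count with the feasibility results.

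**2. Timing.** Sections 7.1 and 8.3 place eligibility before enrolment or study entry. Exclusion 5 cannot be judged then. Excluding a subject from participation during surgery also sits uneasily with the return visits for all subjects in section 7.6.

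**3. Size.** The planned 100 cannot be reproduced: section 9.2 gives a qualitative rationale, with no rate, precision target, alpha or power. The documents also give no exclusion rate and no failure rate, so everything below except the 100 is assumed, and the 100 is used as a convenient base.

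Let 100 procedures be started, k be exclusion-5 cases and f be failures among those kept.

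- Success per procedure kept = (100 − k − f)/(100 − k)
- Success per procedure started = (100 − k − f)/100
- Gap = success per procedure kept × k/100

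| k | f | Per kept | Per started | Gap (points) |
|---|---|---|---|---|
| 0 | any | (100 − f)/100 | same | 0 |
| 1 | 0 | 99/99 = 100% | 99.0% | 1.0 |
| 1 | 3 | 96/99 = 97.0% | 96.0% | 1.0 |
| 1 | 10 | 89/99 = 89.9% | 89.0% | 0.9 |
| 5 | 0 | 95/95 = 100% | 95.0% | 5.0 |
| 5 | 3 | 92/95 = 96.8% | 92.0% | 4.8 |
| 5 | 10 | 85/95 = 89.5% | 85.0% | 4.5 |
| 10 | 0 | 90/90 = 100% | 90.0% | 10.0 |
| 10 | 3 | 87/90 = 96.7% | 87.0% | 9.7 |
| 10 | 10 | 80/90 = 88.9% | 80.0% | 8.9 |

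The gap depends almost entirely on k.

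**4. Other base.** If the 100 are device-use subjects, as section 6.2 counts them, and k excluded cases come on top, the gap is s/100 − s/(100 + k) for s successes. With s = 100 it is 100% − 95.2% = 4.8 points at k = 5 and 100% − 90.9% = 9.1 at k = 10. With s = 95 it is 95.0% − 90.5% = 4.5 and 95.0% − 86.4% = 8.6. The choice of base changes little.

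**The case against.** The best defence is that nothing is hidden. The intra-operative exclusion is in the synopsis and in section 7.1.2, and sections 5 and 6.2 say openly that they concern subjects in whom both devices are used. A device-use population is a legitimate choice for a study of the LRP used with the MSS. The screening log, with its documented reasons for screening failure, might on a natural reading take these cases, so their number could be recovered. The study has no success criterion, so no decision turns on the rate.

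Most of this stands, and it is why the point is minor. It does not answer two things: the plan does not require the number of such cases to appear with the feasibility results, and the undefined term in section 5 lets sites classify the same tried-then-abandoned case differently.

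Some stronger readings are tempting, but the documents do not support them:

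- *These cases go unrecorded.* Several existing records could hold them. The case report forms are not in the documents, so a missing field cannot be shown.
- *Every such case leaves the denominator.* Where the devices were attempted, the subject may remain as an outcome 3 non-success.
- *Experience with the LRP camera arm is lost as well.* Nothing says that arm is in use before the target tissue is assessed.
- *A replacement rule is needed, because section 9.2 speaks of enrolling 100 while section 6.2 counts device use.* The 100 is an unpowered upper limit, and the absence of such a rule is only missing detail.
- *The intent-to-use set must be the main one.* That would change the question asked. Showing both rates is enough.

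**Conclusion.** The point holds as a minor one. Followed as written, exclusion 5 together with the section 5 population can take anatomy-related non-use out of the feasibility rate, and possibly out of the safety summary, without a requirement to report it there. Where this happens, the rate moves in the device's favour or, with no exclusions, stays the same.

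The size is unknown and may be zero. On assumed counts per 100 procedures started, it is about 1 point with 1 exclusion, 4.5 to 5 points with 5 and 9 to 10 points with 10. These figures assume that all k cases are left out. Any tried-then-abandoned case that stays in reduces them.

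The effect is only on how a descriptive rate is read. A reader might take the rate per procedure started as showing how often the system could be used in all elective laparoscopic patients. It does not show that, because surgeons choose whom to enrol (sections 7.1 and 7.2).

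**What to change.** In section 5:

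- Report the number of exclusion-5 cases, with the reason and whether either device had been used or attempted.
- Give feasibility success on two labelled denominators: all consented subjects whose procedure was started with intent to use the LRP and MSS, and procedures in which the devices were used. Say whether an abandoned attempt counts as use.
- Summarise adverse events for all started subjects.

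Elsewhere, reconcile the timing of exclusion 5 with the eligibility statements in sections 7.1 and 8.3, and with the follow-up of all subjects in section 7.6.

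The cost is a few sentences of protocol text, one named place to record the reason and device status (an existing form may serve), slightly more recording, and a possibly less favourable reported rate. No extra subjects are needed.

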7.2 Enrollment and Written Informed Consent

Patients who pass initial pre-screening will be asked to sign the Informed Consent Form (See **Appendix 1**) before any study-specific tests or procedures are performed. The Investigator will inform the potential subject of the elements of the clinical study, including risks, potential benefits and required follow-up procedures, prior to obtaining the potential subject's informed consent. Enrollment may be non-sequential per the discretion of the study surgeon.

7.3 Screening/Baseline Evaluation

The Screening visit will occur within 30 days prior to the laparoscopic procedure.

The following evaluations are required at the time of subject screening /baseline:

- Demographic Information: gender, race, age, weight, and height, and smoking status
- Medical / Surgical History
- Pre-operative blood draw for determination of coagulation disorders if warranted
- Urine pregnancy test for women of childbearing potential. Note that if the screening test is more than 1 week prior to the index procedure, a second urine pregnancy test is required within 7 days of the index procedure.

7.4 Procedure

The Investigator will perform the surgical procedure in accordance with the methods detailed in the Instructions for Use (IFU).

The following intra-operative data will be collected:

- General anesthesia time
- Operative time (from the first incision to the last suture's placement)
- Device and procedure observations
- Number of required surgeons
- Conversion to open surgical procedure

- The need for an additional surgical tool to mobilize the intended organ or tissue
- Estimated blood loss
- Video recording of the overall procedure
- Adverse events

7.5 Post-Procedure / Hospital Discharge

Before hospital discharge the following data will be collected:

- Length of hospital stay (time from admittance to post-anesthesia care unit until hospital discharge)
- Length of time spent in Post Anesthesia Care Unit (PACU)
- Adverse events, if any

7.6 Follow-up

All subjects will be asked to return to the investigational site at 7 days and again at 30 days post-procedure according to the study schedule described in **Table 1**. Subjects will be queried about adverse events at these study visits. Study visits should be scheduled as closely as possible to the earlier part of the time period to allow for rescheduling if needed due to last minute schedule changes. Visits not completed within the specified time period will be regarded as deviations.

Table 1: Schedule of Assessments

Assessment	Time Frame			
	Pre-op	Index Procedure & Discharge	7 day follow-up	30 day follow-up
Visit Window	- 30 days	NA	(± 3 days)	(± 7 days)
Informed Consent	√			
Medical History	√			
Demographics	√			
Blood Tests	√			
Pregnancy Test *	√	√		
Intra-operative assessments		√		
Adverse events		√	√	√

* Urine pregnancy test for all women of childbearing potential at pre-op visit and repeated within 7 days of index procedure unless pre-op visit/prior urine pregnancy test was within 7 days of index procedure.

7.7 Unplanned Follow-up Visits

Subjects returning for unscheduled visits will be reported on the Unscheduled Visit case report form.

7.8 Early Discontinuation / Withdrawal

All subjects will be informed of their right to withdraw from the clinical study at any time without penalty or loss of benefits to which the subject is otherwise entitled. Additionally, the Investigator may prematurely discontinue any subject's participation in the study if the Investigator feels that the subject can no longer fully comply with the requirements of the study or if any of the study procedures are deemed potentially harmful to the subject. The reason for early discontinuation will be documented in the source documents and the Study Termination case report form.

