5.1 Safety Outcomes

All adverse events will be captured and reported. Adverse events will be summarized by relatedness to the device and/or procedure, seriousness and level of severity. If device related, AEs will be further characterized as to relationship to the MSS the LRP or both.

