7.9 Lost to Follow-up Subjects

Every attempt will be made to have all subjects complete the follow-up visit schedule. A subject will not be considered lost to follow-up unless efforts to obtain compliance are unsuccessful. At a minimum, the effort to obtain follow-up information will include three attempts to make contact via telephone or email and if unsuccessful, then a certified letter from the Investigator will be sent to the subject's last known address. In general, the study Site Coordinator should attempt to contact the subject as soon as possible after each missed visit to reschedule the visit.

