8.3 Minimization of Risk and Monitoring Procedures

Levita Magnetics has attempted to mitigate risks as much as possible through product design and development of the MSS which included *in vivo* performance testing, human factors testing, non-clinical performance testing, clinical testing of the MSS in other surgical procedures, biocompatibility testing, sterilization validation, reprocessing validation and shelf life validation. Additionally, careful labeling, IFU and training are provided as detailed below for the MSS and LRP.

Risks will be further mitigated through selection of qualified physicians with competence in minimally invasive surgery, appropriate training, and study monitoring.

- Investigators who participate in the study will be experienced and skilled in laparoscopic surgical techniques. Additionally, Investigators, in conjunction with the investigational site, will have adequate resources for participation in a clinical study.
- The study has been designed to ensure treatment and follow-up of subjects are consistent with current medical practice.
- Each Investigator will ensure oversight and approval of the study by the Ethics Committee (EC) prior to initiation of the clinical study at his/her investigational site.
- The Investigator and study personnel will be trained on the clinical protocol.
- All Investigators who have not previously used the Levita MSS will undergo training with MSS prior to first use during the clinical study.
- All Investigators and operating room support personnel will be provided with a detailed IFU during training and as a reference for review as needed.
 - The IFU details appropriate safety zones for use of the Magnetic Controller in an OR setting and considerations for users of a product with a strong magnet.
- Study personnel are also trained with and receive a “Magnetic Surgery Screening Checklist” and Operating Room (OR) signage to ensure safe use of the system for subjects and users.
- Subjects will be carefully evaluated against the inclusion/exclusion criteria prior to entering the clinical study to ensure that their diagnosis and medical status are appropriate for participation in the clinical study.

- Subjects will be monitored up to the 30-day follow-up visit as defined in the study protocol. The follow-up visit will be with an Investigator to monitor the subjects' status.
- A study Investigator will evaluate the subject for any adverse events potentially related to the device.

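### Section 7.8 lets the Investigator discontinue a subject after the single device use, with no adverse-event check from then to day 30

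*Combined protocol and SAP*

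**What the plan says.** Section 7.8 provides that "the Investigator may prematurely discontinue any subject's participation in the study if the Investigator feels that the subject can no longer fully comply" with what the study asks, or if a study procedure is judged potentially harmful. The rule has no time limit, so it can be applied before or after surgery. On documentation it says: "The reason for early discontinuation will be documented in the source documents and the Study Termination case report form". It asks for no AE query at exit and no later contact.

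Section 7.6 sets the follow-up: "All subjects will be asked to return to the investigational site at 7 days and again at 30 days post-procedure". AEs are asked about at those visits. In Table 1, AEs are the only item scheduled at day 7 (±3 days) and day 30 (±7 days).

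Section 7.9 deals with subjects who miss visits. It says "Every attempt will be made to have all subjects complete the follow-up visit schedule" and sets a floor: "At a minimum, the effort to obtain follow-up information will include three attempts to make contact via telephone or email", then a certified letter. It adds that "the study Site Coordinator should attempt to contact the subject as soon as possible after each missed visit to reschedule the visit".

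On the safety outcome, Section 5 evaluates endpoints in every subject operated on with the Levita Robotic Platform (LRP) and the Magnetic Surgical System (MSS). Section 5.1 says "All adverse events will be captured and reported", and Section 8.3 lists among the risk controls that "Subjects will be monitored up to the 30-day follow-up visit as defined in the study protocol". Section 9 is descriptive and has no rule for denominators or for incomplete 30-day safety data.

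**The concern.** Exposure here is a single event. Once the operation is over there is no further device use to stop, and after discharge the scheduled assessments are the two AE queries. Ending a subject's participation at that stage takes the subject out of scheduled safety ascertainment and spares no further exposure.

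The ground for doing so, inability to comply fully, may be related to the outcome. Follow-up is on site and follows surgery, so a subject who cannot travel, or is in another hospital, is one who could be judged unable to comply. Loss of that kind would not be random with respect to AEs. In a single-arm study whose stated purpose is safety and feasibility, there is no control group against which such a loss would show.

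**Working it through.** There is no planned figure to reproduce: Section 9.2 justifies 100 subjects without an event rate, a precision target or a dropout allowance. The check is therefore mainly of the text, with an illustration of size.

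**1. What a discontinued, exposed subject still has**

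| Provision | Covers | Does not cover |
|---|---|---|
| 7.4, 7.5 | AEs during surgery and up to discharge | Events after discharge |
| 7.6, Table 1 | AE queries at days 7 and 30 | Subjects no longer participating |
| 7.7 | Subjects who come back unscheduled | Subjects who do not return to the site |
| 7.9 | Subjects who miss visits | Subjects discontinued under 7.8 |
| 12.1.1, 12.1.2, 12.2 | Recording and reporting of AEs and serious AEs the site learns of; follow-up of reported, ongoing AEs | Events the site has not heard of |
| 12.5 | Deaths during the investigation, once the Investigator knows | Unclear whether a discontinued subject counts |

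What is left uncovered is a new or not-yet-reported event between Investigator-initiated discontinuation and day 30.

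**2. Bounds on the AE rate (all inputs assumed except the planned maximum of 100)**

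Let N = 100 be the number exposed, d the number discontinued with no recorded event and unknown status to day 30, and x the number of subjects with a recorded event. The share of exposed subjects with an event lies between x/N and (x + d)/N, a width of d/N. With d = 5:

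- The width is 5/100 = 5 percentage points, whatever x is.
- If x = 0, the range is 0/100 = 0% to 5/100 = 5%. An analysis of the 95 followed gives 0/95, with an exact 95% upper limit of 3.8%. That limit reflects sampling error only and lies below the 5% worst case.
- If x = 8, the 95 followed give 8/95 = 8.4%, and the range is 8/100 = 8% to 13/100 = 13%. The 8.4% is inside the range, not below it.

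**3. Direction (assumed loss rates)**

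Let p be the true rate, a the fraction of subjects with an event who are discontinued before it is recorded, and b the fraction of event-free subjects who are discontinued. The rate among those followed is p(1 − a) / [p(1 − a) + (1 − p)(1 − b)]. With p = 10%:

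- a = 30%, b = 2%: 0.07 / (0.07 + 0.882) = 7.4%. The expected number discontinued is 10 × 0.30 + 90 × 0.02 = 4.8 of 100.
- a = 50%, b = 2%: 0.05 / (0.05 + 0.882) = 5.4%.
- a = b = 2%: 0.098 / (0.098 + 0.882) = 10%, so no bias.
- a = 0, b = 5%: 0.10 / (0.10 + 0.855) = 10.5%, a slight overstatement.

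Understatement thus needs a greater than b. Dividing by all 100 exposed does not repair the loss by itself: in the first case it gives 7/100 = 7%. The status has to be collected, or the number unknown has to be shown.

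**The case against.** The best case for the plan is that most of the obvious scenario is already covered. An Investigator who discontinues a subject because of a complication knows of the complication. It must be recorded under 12.1.1, reported within 24 hours if serious, and followed under 12.2 while ongoing. Section 7.8 is permissive, also serves for the period before surgery, and does not say that AE collection stops. The study is descriptive, with no test or safety threshold to distort. All of this stands, and it narrows the gap to events the site has not heard of. It does not close the gap, because nothing obliges anyone to ask.

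A reader might infer several stronger points that the documents do not support:

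- *That 7.9 seeks only to rebook visits.* Its minimum effort is directed at follow-up information, by telephone, email and certified letter. What it lacks is a statement that AE status may be taken remotely in place of a visit.
- *That 7.8 contradicts 5.1 and 8.3.* It allows an exit without saying how those commitments are then met. That is a gap in the rule, not opposing statements.
- *That 7.8 is aimed at subjects too ill to comply.* Illness is not named; that reading is an inference from on-site visits after surgery.
- *That discontinuation removes nothing but safety follow-up.* Recovery-unit time and length of stay are collected up to discharge (7.5), and patient satisfaction is listed in 5.3 without a scheduled time. The statement is true only of what Table 1 schedules after discharge.

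**Conclusion.** The point holds in a limited form. Under 7.8 an exposed subject can be discontinued by the Investigator with only the reason recorded. From then to day 30, no provision requires new or unreported AEs to be sought, and Section 9 does not say how such a subject is counted.

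A reader might go further and conclude that the safety result will be biased downward. That is plausible but not shown. It requires discontinued subjects to have more events than those followed, and the bounds above include values below the rate seen in those followed. The size is unknown, because the documents give neither event nor discontinuation rates. Each exposed subject with no recorded event and unknown 30-day status leaves one percentage point of 100 unresolved, so an assumed 5 leave up to 5 points. The 5 is an assumption, and so is treating those subjects as wholly unobserved after discontinuation. The wording of the consent form was not available, so what it allows after discontinuation could not be checked.

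This is a cheap improvement worth making, not a flaw that undermines the study.

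**What to change.** - **Section 7.8:** state that once the LRP or MSS has been used, discontinuation by the Investigator does not end AE collection unless the subject withdraws consent. Require an AE query at discontinuation, and an AE and vital-status check at day 30 by telephone or from records, as consent permits. Check that the consent form allows this.
- **Section 7.9:** as a clarification, say that AE status may be taken remotely when a missed visit cannot be rebooked.
- **Section 9:** keep all exposed subjects in the AE denominator. Beside the AE rates, report how many lack complete 30-day AE status, with reasons.

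The cost is a few sentences, one CRF field, and an occasional extra call or records check. No additional subjects or visits are needed.
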